Statistical analysis plan

Identifying the active elements of a digital single-session intervention targeting depression: a factorial experiment

ClinicalTrials.gov ID: NCT06322849

May 1, 2024

Arms and Interventions: details

We will conduct an 8-arm factorial trial to determine the main and interaction effects of the candidate components. The 8 conditions are provided in Table 1.

	Breathing	Psychoeducation	Testimonials + Saying is believing exercises	Action plan
Condition 1	Yes	No	No	No
Condition 2	Yes	No	No	Yes
Condition 3	Yes	No	Yes	No
Condition 4	Yes	No	Yes	Yes
Condition 5	Yes	Yes	No	No
Condition 6	Yes	Yes	No	Yes
Condition 7	Yes	Yes	Yes	No
Condition 8	Yes	Yes	Yes	Yes

Table 1

Breathing – This component will present a triangle breathing video for 2 minutes and will be present in all 8 conditions.

Psychoeducation – This component provides information on how taking action can help improve our mood and different types of actions participants can take to improve their mood.

Testimonials + Saying is believing exercises – Participants are shown examples of how other individuals have taken action to improve their mood. The participant is also asked to provide advice to another simulated individual who is stuck in a *negative mood spiral*.

Action plan – The participant is walked through to plan the details of a positive action that they want to take to improve their mood.

Randomization

Participants will be randomized to one of the 8 conditions with equal probability using Qualtrics's internal randomizer.

Data collection and sample size

Data collection procedures

We will recruit participants through the CloudResearch Connect platform. All potential participants will be paid \$0.25 for completing a 2-minute screener of depressive symptoms to determine their eligibility for the study. Eligible participants will be paid \$3.00 for completing the first part containing the baseline questionnaires, 1 of the 8 conditions, and immediate post-intervention questionnaires (18 minutes). They will be compensated \$1.00 for completing the 2-week follow-up (5 minutes), and \$1.00 for completing the 8-minute follow-up (5 minutes). Payment will be delivered online through CloudResearch Connect.

Sample size

We will recruit 880 participants with 110 participants in each group.

Sample size rationale

We aimed to detect a main effect of Cohen's d = 0.15 for the candidate components (we considered d=0.15 as the minimum acceptable effect size for a candidate component to be independently useful). We calculated the sample size using the MOST package in R, which performs power calculations using simulated data.

Stopping rule

We will stop the trial when we have reached the required number of participants.

Analysis plan

Demographic data

We will report demographic variables as percentages of the total number of participants.

Effects of candidate components and common factors

We will run 3 separate multiple regressions with the PHQ-8 score at immediate post-intervention, 2week follow-up, and 8-week follow-up as the dependent variable and baseline PHQ-8 and the effectcoded candidate components as the predictors (Collins et al., 2014). We will use the *stats* package in R to run the regression.

Im(8-week PHQ-8 ~ baseline PHQ-8 + (mainEffectPsychoeducation + mainEffectSIBT + mainEffectActionPlan)^3)

SIBT = Saying is believing + Testimonials

As an exploratory analysis, we will repeat the above multiple regression and include credibility rating and expectancy rating at immediate post-intervention as predictors.

Im(8-week PHQ-8 ~ baseline PHQ-8 + (mainEffectPsychoeducation + mainEffectSIBT + mainEffectActionPlan)^3 + credibility rating + expectancy rating)

We will run another exploratory analysis with 8-week PHQ-8 as the dependent variable and baseline PHQ-8 and effect-coded candidate components as predictors, and we will include all the demographic variables as co-variates.

Im(8-week PHQ-8 ~ baseline PHQ-8 + (mainEffectPsychoeducation + mainEffectSIBT +
mainEffectActionPlan)^3 + gender + age + ethnicity + sexual orientation + educationLevel + employment
+ MacArthurScaleofSubjectiveSocialStatus + programCompletiondevice)

We will also run 4 separate multiple regressions with measures of hopelessness (BHS-4), autonomy, relatedness, and competence (BMPN) as dependent variables and the effect-coded candidate components as predictor variables.

The regression coefficients will provide the main and interaction effects of the candidate components (Kugler et al., 2018).

Mediation effects of autonomy, relatedness, and competence

To evaluate the mediation effects of autonomy, relatedness, and competence, we will use the joint significance test (MacKinnon et al., 2002). It is a causal steps approach to evaluate mediation effects. It tests two null hypotheses: the effect of the mediator on the dependent variable is 0 (*b* pathway), and the effect of the independent variable on the mediator is 0 (*a* pathway). If the effects of both the *b* and *a* pathway are significantly different from 0, it is considered evidence for mediation (Strayhorn et al., 2022). We will separately evaluate whether autonomy, relatedness, and competence:

- 1. at immediate post-intervention mediates the PHQ-8 scores at 2-week and 8-week follow-up
- 2. at 2-week follow-up mediates the PHQ-8 score at 8-week follow-up.

Inference criteria

To determine statistical significance of the candidate components, we will use $\alpha = 0.10$ to reduce the risk of ruling out potentially active ingredients (Watkins et al., 2023).

For all other analyses, we will use α = 0.05. We will use two-tailed tests for all analyses.

Data exclusion

We will exclude participant data if they:

- 1. dropped out before being randomized to one of the 8 conditions
- 2. indicate that they did not participate seriously in the study
- 3. complete the study more than once. In such cases, if possible, we will use data from the first submitted survey.

Missing data

We will take efforts to avoid missing data (e.g., a financial incentive for completing the study and reminder emails). Participants with missing data at will be included in the analysis and missing data will be imputed using the multiple imputation method. We will use the mice package in R for multiple imputation.

Exploratory analysis

Additionally, we will run exploratory analyses using data generated from this study. However, we are not pre-registering these exploratory tests at this time.

References

Collins, L. M., Dziak, J. J., Kugler, K. C., & Trail, J. B. (2014). Factorial Experiments. American Journal of

Preventive Medicine, 47(4), 498–504. https://doi.org/10.1016/j.amepre.2014.06.021

Kugler, K. C., Dziak, J. J., & Trail, J. (2018). Coding and Interpretation of Effects in Analysis of Data from a

Factorial Experiment. In L. M. Collins & K. C. Kugler (Eds.), Optimization of Behavioral,

Biobehavioral, and Biomedical Interventions (pp. 175–205). Springer International Publishing. https://doi.org/10.1007/978-3-319-91776-4_6

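### Free improvement: the four BHS-4 and BMPN regressions leave out baseline PHQ-8, which the SAP's PHQ-8 regressions include; estimates stay unbiased but some precision is lost

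*SAP*

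**What the plan says.** All of the following is in the SAP.

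- **PHQ-8 models** (Effects of candidate components and common factors). The regressions at immediate post-intervention, 2 weeks and 8 weeks use "baseline PHQ-8 and the effectcoded candidate components as the predictors". Both exploratory PHQ-8 models do the same. The formula with credibility and expectancy contains baseline PHQ-8, and the demographic model is described as "another exploratory analysis with 8-week PHQ-8 as the dependent variable and baseline PHQ-8 and effect-coded candidate components as predictors". That makes five models, all adjusted for baseline PHQ-8.
- **Hopelessness and BMPN models** (same section). Four further regressions take "measures of hopelessness (BHS-4), autonomy, relatedness, and competence (BMPN) as dependent variables and the effect-coded candidate components as predictor variables". No formula is given, and nothing elsewhere in the SAP adds a baseline covariate for these outcomes.
- **Baseline data** (Data collection procedures). Part one of the study is the "first part containing the baseline questionnaires, 1 of the 8 conditions, and immediate post-intervention questionnaires (18 minutes". The scales in the baseline set are not listed. Baseline PHQ-8 must be among the baseline data because five models use it; baseline BHS-4 and BMPN are not mentioned.
- **Mediation.** Autonomy, relatedness and competence are to be tested for whether each "at immediate post-intervention mediates the PHQ-8 scores at 2-week and 8-week follow-up" and "at 2-week follow-up mediates the PHQ-8 score at 8-week follow-up".
- **Benchmark** (Sample size rationale). The trial is sized on d = 0.15: "we considered d=0.15 as the minimum acceptable effect size for a candidate component to be independently useful".

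**The concern.** Within one section, baseline PHQ-8 is used for one outcome and dropped for four others, and no reason is given. It is measured before the intervention, so it is a legitimate covariate for any later outcome. Leaving it out does not bias a randomised comparison, but it forgoes whatever precision the covariate would bring and gains nothing in return.

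The loss runs against the SAP's own aim. Under Inference criteria, alpha for the components is relaxed to 0.10 so that active components are not missed. It may also matter for mediation: the joint significance test requires a significant effect of the component on the mediator, and three of these four outcomes are the mediators. The SAP does not write out the component-to-mediator models. Three mediators at two time points make six models, so the three BMPN regressions cannot be the full set, and the covariates in the mediator models are unstated.

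**Working it through.** **Inputs from the SAP.** N = 880, as 8 × 110; equal allocation, so each main effect compares 440 with 440; d = 0.15; two-sided tests; alpha 0.10 for the candidate components and 0.05 for all other analyses. Both alphas are shown, because the SAP does not say explicitly which applies to these four outcomes.

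**Assumed.** The correlation r between baseline PHQ-8 and the outcome (the SAP gives none), taken as 0.2, 0.3 and 0.5; complete data on all 880. The SAP sets no detectable effect for BHS-4 or BMPN, so d = 0.15 serves only as a benchmark. There is no stated precision figure for these models to reproduce.

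**Step 1, unadjusted model.** In outcome SD units, the standard error of a main effect is √(1/440 + 1/440) = 0.0674. The noncentrality is 0.15 / 0.0674 = (0.15/2) × √880 = 2.225. The full 2³ model has 8 coefficients, leaving 880 − 8 = 872 degrees of freedom. Power from the noncentral t is 60.4% at alpha 0.05 and 71.9% at 0.10.

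**Step 2, add one baseline covariate.** The residual SD becomes √(1 − r²) of its former value, so the standard error is multiplied by √(1 − r²) and the noncentrality is divided by it; 871 degrees of freedom remain. The equivalent unadjusted sample size is 880 / (1 − r²).

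| r (assumed) | SE multiplier | Noncentrality | Power, alpha 0.05 | Power, alpha 0.10 | Equivalent N |
|---|---|---|---|---|---|
| 0 | 1 | 2.225 | 60.4% | 71.9% | 880 |
| 0.2 | 0.980 | 2.271 | 62.1% | 73.4% | 917 |
| 0.3 | 0.954 | 2.332 | 64.4% | 75.4% | 967 |
| 0.5 | 0.866 | 2.569 | 72.8% | 82.2% | 1173 |

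**Step 3, effect detectable with 80% power.** This scales by the same multiplier:

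- alpha 0.05: from d = 0.189 to 0.185, 0.180 and 0.164 for r = 0.2, 0.3 and 0.5;
- alpha 0.10: from d = 0.168 to 0.164, 0.160 and 0.145.

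**Step 4, checks by simulation of the eight-cell design with N = 880.**

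- Bias (3,000 runs per value of r, true effect 0.15): the mean estimated effect lay between 0.147 and 0.152 both with and without the covariate, so neither model is biased.
- Precision (same runs): the ratio of empirical standard errors was 0.979, 0.954 and 0.850 for r = 0.2, 0.3 and 0.5, close to √(1 − r²).
- Power (6,000 runs per cell): adjusted power was 0.625, 0.643 and 0.728 at alpha 0.05, and 0.738, 0.754 and 0.822 at alpha 0.10.

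**Conditional case, not counted in the size.** If the outcome's own baseline was measured and correlates at 0.7 (assumed), power would be about 88% at alpha 0.05 and 93% at 0.10. The SAP does not say that these baselines are collected.

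**The case against.** The strongest case against is that nothing here is wrong. The unadjusted tests are valid, the SAP nowhere promises adjustment for these outcomes, and adjusting for the baseline of a different construct is partly a matter of taste. That stands, and it is why the point is optional.

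The benefit also rests on an assumed correlation. At r = 0.2 the gain is under 2 percentage points of power. At r = 0.1 the standard error falls by only 0.5%. Selection on depressive symptoms may narrow the range of baseline PHQ-8 and push r down, so the r = 0.5 row should be read as an upper illustration. This also stands. The power figures further assume complete data, whereas the SAP plans exclusions and multiple imputation. They illustrate the loss; they do not measure it in this trial.

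It can also be said that the sentence is shorthand, since it omits the interactions too, although the next sentence says that the coefficients give main and interaction effects. But the PHQ-8 sentence names its baseline covariate and this one does not, so an analyst following the text would fit these models without it.

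None of these is a reason to leave the covariate out. Even if r is small, the cost is one degree of freedom in 872.

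**Conclusion.** The concern holds as an optional, nearly free improvement. The SAP adjusts for baseline PHQ-8 in all five PHQ-8 regressions of that section and in none of the four BHS-4 and BMPN regressions. The unadjusted component effects are unbiased under randomisation with complete data; with dropout this also depends on the imputation model.

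The loss is one of precision only. At r = 0.2 to 0.3, the more plausible end, the standard errors are needlessly larger by an amount that adjustment would cut by 2% to 5%. That is worth about 37 to 87 participants (917 − 880 and 967 − 880). At r = 0.5 the cut is 13%, worth about 293 participants (1173 − 880). All of this depends on correlations that the SAP does not give, and on d = 0.15 being borrowed as the benchmark.

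**What to change.** Add baseline PHQ-8 to all four regressions, and add the baseline score of the same scale only where it was measured:

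outcome at time t ~ baseline PHQ-8 [+ baseline of the same outcome] + (psychoeducation + SIBT + action plan)^3

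State the time point t, which the SAP does not give for these four regressions. Use the same covariates in the models of component effects on autonomy, relatedness and competence at immediate post-intervention and at 2 weeks, so that the mediation analysis follows the same rule.

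The cost is one line in the SAP, no new data, and one or two degrees of freedom (872 falls to 871 or 870). The change should be made before outcome data are examined, so that the covariate set is not chosen after the fact.

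### Does the SAP test the same component effect on a mediator at two significance levels, 0.10 and 0.05?

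*SAP*

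**What the plan says.** Three parts of the SAP bear on this.

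- **Effects of candidate components and common factors.** After the PHQ-8 models, the SAP adds: "We will also run 4 separate multiple regressions with measures of hopelessness (BHS-4), autonomy, relatedness, and competence (BMPN) as dependent variables", with the effect-coded components as predictors. It then says: "The regression coefficients will provide the main and interaction effects of the candidate components". No time point is given for these four regressions.
- **Mediation effects of autonomy, relatedness, and competence.** The joint significance test has two null hypotheses. For the a-pathway the null is that "the effect of the independent variable on the mediator is 0". The decision rule is: "If the effects of both the *b* and *a* pathway are significantly different from 0, it is considered evidence for mediation". No significance level stands beside either pathway. The mediators are needed at two time points, immediately after the intervention and at 2 weeks.
- **Inference criteria.** "To determine statistical significance of the candidate components, we will use" α = 0.10, with the stated aim of not discarding components that may be active. Then: "For all other analyses, we will use α = 0.05". Finally: "We will use two-tailed tests for all analyses".

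**The concern.** The 0.10 rule is not limited to PHQ-8. The BMPN regressions stand under the heading on component effects, and their coefficients are described as component effects, so 0.10 seems to apply to them. The a-pathway is the effect of a component on one of the same three scales, and the SAP prints no separate model for it. As part of mediation it seems to fall under the 0.05 sentence. One coefficient would then carry two levels.

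What would be at stake is the mediation result. When the b-pathway is significant, the a-pathway alone decides whether mediation is declared. If the text truly left the level open, it could be chosen after the p-values were known.

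**Working it through.** **1. The plan's own figure.** The SAP plans 880 participants, 110 in each of 8 conditions, so each component main effect compares 4 × 110 = 440 with 440. The target is d = 0.15. The standard error of a standardised difference is √(2/440) = 0.0674, so z = 0.15/0.0674 = 2.225. Two-sided power is 71.9% at α = 0.10 and 60.4% at α = 0.05. The SAP states no power, so 880 cannot be strictly reproduced. With an assumed baseline correlation of 0.45, 80% power at 0.10 needs 878. That gain belongs to the PHQ-8 models, which adjust for baseline; the four other regressions are described with the components as the only predictors. The unadjusted figures therefore apply below.

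**2. Width of the disputed zone.** The smallest significant observed difference is 1.645 × 0.0674 = 0.111 at α = 0.10 and 1.960 × 0.0674 = 0.132 at α = 0.05. Only results between these two values are in question.

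**3. Chance that one test falls in the zone** (normal approximation):

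| True d on the mediator | Significant at 0.10 | Significant at 0.05 | In the zone |
|---|---|---|---|
| 0 | 10.0% | 5.0% | 5.0% |
| 0.10 | 43.7% | 31.7% | 12.0% |
| 0.15 | 71.9% | 60.4% | 11.5% |
| 0.20 | 90.7% | 84.3% | 6.4% |
| 0.30 | 99.8% | 99.4% | 0.4% |

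Simulating the full 2 × 2 × 2 effect-coded regression (20,000 runs, 110 per cell) gave 4.8% in the zone at d = 0 and 11.8% at d = 0.15.

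**4. How many coefficients could be tested twice.** Mediation uses 3 components × 3 mediators × 2 mediator time points = 18 main-effect a-pathways. The SAP lists only three BMPN regressions besides the BHS-4 one, with no time point. Run once each, they give 3 × 3 = 9 main-effect coefficients, and these are a-pathways only if the time point matches. If all effects are null and the tests are treated as independent (an assumption), the chance that at least one falls in the zone is:

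- 1 − 0.95^18 = 60% if all 18 a-pathways were also tested as component effects;
- 1 − 0.95^9 = 37% if the three regressions are run at one matching time point;
- zero if they are run at a time point that mediation does not use, such as 8 weeks.

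**5. What each level does to the mediation test.** If the a-pathway is null, the false-positive rate is α times the chance that the b-pathway is significant. It is at most 5% at α = 0.05 and at most 10% at α = 0.10. With d = 0.15 on the mediator, and an assumed 80% power for the b-pathway independent of the a-pathway, joint power is 0.80 × 60.4% = 48% at 0.05 and 0.80 × 71.9% = 58% at 0.10.

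**6. The sentences side by side.** The 0.10 sentence concerns whether a component is active. The 0.05 sentence covers everything else. Whether a component works through autonomy is a different question, with its own heading and its own two-part rule. Read in order, the text places it under the second sentence. Two analysts reach opposite mediation verdicts only if one of them brings the component rule into the mediation test, which the SAP does not tell them to do.

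**The case for a change.** The strongest opposing case is that the a-pathway is itself a component effect. The reason given for 0.10, not ruling out active ingredients, could be said to cover it, and nothing limits that rule to PHQ-8. A reader could coherently carry 0.10 into the a-pathway and keep 0.05 for the b-pathway. The Inference criteria section exists to allocate α, so it should leave no room for this.

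Part of this stands: the SAP names no level beside either pathway, and one sentence would have closed the question. The rest is weaker. The catch-all sentence does give an answer for mediation. Nothing in the SAP requires one coefficient to carry one level across two different questions. That the BMPN regressions supply the a-pathways is a reasonable inference, but the missing time point means they need not supply all of them, or any.

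The possible remedies offer no clear gain. Writing 0.05 beside both pathways repeats the present text. Writing 0.10 for the a-pathway doubles the maximum false-positive rate in exchange for 11.5 percentage points of a-pathway power at d = 0.15. Limiting 0.10 to PHQ-8 would make the component tests on BHS-4 and the BMPN scales stricter, a substantive change that goes beyond the ambiguity.

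**Conclusion.** No change to the plan is needed. As written, mediation is tested at 0.05 on both pathways and component effects at 0.10. A component effect on a mediator with p between 0.05 and 0.10 can be reported as passing the component screen and as not meeting the mediation criterion, and both statements are correct under their own rules.

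What remains is a small gap in wording that analysts can fill from the catch-all sentence. It concerns about 5% of null a-pathways and 11.5% of those with a true difference of 0.15, and then only where the b-pathway is significant. These figures assume 440 against 440 with complete data, no covariate gain, and that the SAP's target effect applies to the mediators. The counts across many tests are illustrative, because they depend on a time point that the SAP does not give. The PHQ-8 component tests are unaffected.
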